#### **8.2 Patient demographics and other baseline characteristics**

Demographic and baseline characteristics will be summarized descriptively for the safety population. Continuous variables will be summarized by mean, standard deviation, median, minimum, maximum, and number of subjects with non-missing data. Categorical variables will be summarized by absolute frequencies and percentages.

#### **8.3 Treatments**

The exposure to study drug (number of injections) and duration of exposure (days) will be summarized and listed.

## **8.4 Analysis of the primary variable(s)**

### **8.4.1 Variable(s)**

Percentage of complete responders.

Symptoms measured by VAS.

Percentage of patients achieved appropriate steroid tapering.

Changes of general disease activity measured by BDCAF.

### **8.4.2 Statistical model, hypothesis, and method of analysis**

To claim the efficacy of canakinumab on the resolution of attacks, at least 50% response will be aimed in at least 50% of the patients.

All parameters will be compared with baseline values. Complete / Partial / Non responders definitions can be seen in efficacy assessment section.

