## 2.1 Primary objective(s)

**Primary endpoint:** Resolution of acute exacerbation findings related to BD based on achievements in any of the following items without deterioration on day 30:

**For patients with parenchymal neurologic disease:** Resolution of acute exacerbation of parenchymal neurologic findings based on improvements in any of the following items without deterioration on Day 30:

- a. Improvement of muscle strength, ataxia, or other relevant neurologic findings depending on the involved region on neurological examination (by NBDS, Modified EDSS, and modified Rankin scores)
- b. Improvement in systemic inflammatory findings (CRP, ESR, SAA)
- c. Any decrease in the size of the MRI lesion, or disappearance of contrast enhancement
- d. Improvement in patients' and physicians global assessment using a 10-cm visual analogue scale (VAS)

**Complete response** will be defined as full clinical recovery to the pre-attack state, disappearance of MRI lesion(s), and normalisation of CSF findings.

**Partial response** will be defined as partial improvement in clinical findings, but with findings still worse than the pre-attack state, and MRI lesions, which become smaller with no or less enhancement, and a decrease in CSF cell count.

**Non-response** will be defined as no improvement in clinical findings, no change on MRI, no change in CSF parameters, or worsening in those findings.

**For patients with large vessel vascular disease:** Resolution of acute vascular exacerbation findings related to BD based on achievements in any of the following items without deterioration at 1 month:

- a. Improvement in relevant symptoms (localised pain, abdominal pain, calf thickness, haemoptysis) by using physician and patient's global assessment with VAS
- b. Improvement in systemic inflammatory findings (CRP, ESR, SAA)
- c. Any improvement in radiological findings depending on the involved vessels (MR, CT or Doppler findings)
- d. Improvement in patients' and physicians global assessment using a 10-cm visual analogue scale (VAS)

**Complete response** will be defined as clinical and laboratory improvement based on  $\geq 50\%$  improvements in patient's and physician's global assessments by using VAS, and  $\geq 50\%$  reduction in CRP values; along with stable or  $\geq 20\%$  reduced aneurym size in patients with arterial involvement, and stable or  $\geq 20\%$  reduced calf swelling in patients with lower extremity venous thrombosis.

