## 2.2 Secondary objectives

### Secondary endpoints:

#### General :

Overall disease activity measures (BDCAF-Behçet's Disease Current Activity Form)

Reduced need for corticosteroid treatment (reduction of corticosteroid dosage)

Course of other BD-related manifestations

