#### **1-For Neuro Behcet Attack**

- A Improvement of muscle strength (Measured by MRC, and VAS)
- B Ataxia (Measured by global assessment of Physician)
- C Modified EDSS (Modified Expanded Disability Status Scale) , Neuro-Behçet's Disability Score (NBDS) **ranging from 0-8 and the modified Rankin scores (0-6)**
- D Improvement in systemic inflammatory findings (CRP, ESR, SAA)
- E Any decrease in the size of the MRI lesion, or disappearance of contrast enhancement

**Complete response** will be defined as full clinical recovery to pre-attack state, disappearance of MRI lesion(s), CSF becomes normal.

**Partial response** will be defined as partial improvement in clinical findings, but with findings still worse than pre-attack state, MRI lesions which become smaller with no or less enhancement, and a decrease in CSF cell count.

**Non-response** will be defined as no improvement in clinical findings, no change on MRI, no change in CSF parameters, or worsening in those findings.

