## **8.5 Analysis of secondary variables**

### **8.5.1 Efficacy variables**

Kaplan-Meier estimates will be presented for time to relapse.

Continuous endpoints (steroid tapering, VAS scores, BDCAF scores) will be summarized by mean, standard deviation, median, median, interquartile range, minimum and maximum.

Differences between pre-treatment and post-treatment values will be analysed by the non-parametric Wilcoxon signed rank test at the 0.05 level of significance.

Correlations between the different parameters will be explored by Spearman's rank correlation coefficient.

Categorical variables will be summarized by absolute frequencies and percentages.

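### The primary efficacy result is not fixed: Sections 2.1/5.9.1 and 8.4.1 name different primary measures, and the 8.4.2 efficacy rule uses a response with no defined meaning for neurologic patients

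*Combined protocol and SAP*

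**What the plan says.** **Primary endpoint.** Sections 2.1 and 5.9.1 of the protocol both define it as "Resolution of acute exacerbation findings related to BD based on achievements in any of the following items without deterioration on day 30". Item lists follow for neurologic and vascular patients, and in each a fall in inflammatory markers is one qualifying item. Both sections then add complete, partial and non-response categories without saying which category is success. Section 3.4 says that the physician assesses the primary endpoint at the end of month 1 and that the categories will be determined then. It does not name a success category either.

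**Primary variables.** Section 8.4.1 lists four: "Percentage of complete responders", VAS symptoms, "Percentage of patients achieved appropriate steroid tapering", and change in BDCAF. They have no order and no time point.

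**The same measures as secondary.** Section 2.2 lists BDCAF and "Reduced need for corticosteroid treatment (reduction of corticosteroid dosage" among the secondary endpoints. Section 8.5.1, on secondary variables, states: "Continuous endpoints (steroid tapering, VAS scores, BDCAF scores) will be summarized by mean" and other descriptive statistics.

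**Efficacy rule.** Section 8.4.2 reads "To claim the efficacy of canakinumab on the resolution of attacks, at least 50% response will be aimed in at least 50" percent of the patients, and adds: "Complete / Partial / Non responders definitions can be seen in efficacy assessment section". In that section, complete response for neurologic patients is "full clinical recovery to pre-attack state, disappearance of MRI lesion(s), CSF becomes normal". Their partial and non-response categories are also qualitative.

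**Analysis sets.** Section 8.1 presents an intent-to-treat (ITT) set of everyone dosed at least once, and a per-protocol set of study completers without major deviations. Sections 3.1 and 5.5.5 drop non-responders at month 1.

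**The concern.** A reader who follows Sections 2.1 and 5.9.1 and a reader who follows 8.4.1 would report different headline results from the same data. A reader who tries to apply 8.4.2 to a neurologic patient finds no defined quantity to compare with 50%. The trial is open label and the physician judges response, so an unfixed definition and denominator leave room for the choice to be made once results are known. At stake is whether the trial can say, on a basis set in advance, that its one stated efficacy criterion was or was not met.

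**Working it through.** The plan gives no response rate, no split between neurologic and vascular patients, and no calculation behind its sample size of 10 (Section 8.7), so there is no planned figure to reproduce. All patient counts and rates below are assumptions. The definitions, the cut-offs and the rule that non-responders are dropped come from the protocol.

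**1. Do the primary measures agree?** The any-item endpoint of 2.1 and 5.9.1 does not appear in 8.4.1. Of the four variables in 8.4.1, two (BDCAF and steroid reduction) are secondary in 2.2, and three (VAS, steroid tapering and BDCAF) are analysed as secondary in 8.5.1. Steroid tapering cannot be a Day 30 result: under 5.9.4 it starts at Day 30 and its target falls at Day 120. Section 8.6 schedules four analyses (Days 30, 90, 180 and 360), and neither 8.4.1 nor 8.4.2 says which one carries the claim.

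**2. Does it change the answer?** Take 10 vascular patients with global VAS and CRP each down 45%, stable imaging and nothing worse. All meet the any-item endpoint. All are partial responders in both 2.1 (20-49%) and 5.9.1 (20-50%).
- Any-item: 10/10. Exact lower 95% limit = 0.025^(1/10) = 0.6915, so 69.2% to 100%.
- Complete response: 0/10. Exact upper 95% limit = 1 − 0.6915 = 0.3085, so 0% to 30.8%.

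Ten neurologic patients who improve but stay worse than before the attack, with smaller lesions and a lower CSF cell count, give the same 10/10 and 0/10.

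A mixed case also crosses the 50% line. With 3 complete, 5 partial and 2 non-responders, complete response is 3/10 = 30% (exact 95% CI 6.7% to 65.2%). Complete-or-partial response, used here as a proxy for any-item, is 8/10 = 80% (44.4% to 97.5%).

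**3. How often would the verdicts differ?** Read the rule as at least 5 of 10. Complete responders are a subset of complete-or-partial responders, so

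P(verdicts differ) = P(at least 5 complete or partial) − P(at least 5 complete).

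With assumed true rates of 30% complete and 40% partial, this is 0.953 − 0.150 = 0.80. Over the assumed complete/partial pairs 20/40, 30/40, 40/40, 30/50 and 20/60 (percent), it runs from 0.63 to 0.96.

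**4. What is a 50% response?** For vascular patients it roughly matches complete response. Even there, a change of exactly 50% is complete in 2.1 (at least 50%) and partial in 5.9.1 (more than 50% is needed for complete). For neurologic patients, no category in 2.1 or 5.9.1 carries a percentage. The only neurologic 50% is a secondary item in 2.2, the time to 50% resolution of the MRI lesion. It refers back to a definition that the preceding text does not contain.

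**5. Which denominator?** Assume 4 complete, 2 partial and 4 non-responders dropped at month 1, and assume also that all six continuing patients complete the study without major deviations. For complete response:
- ITT: 4/10 = 40% (exact 95% CI 12.2% to 73.8%), below 50%.
- Per protocol: 4/6 = 67% (22.3% to 95.7%), above 50%.

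**6. How much can the rule support?** A result exactly on the threshold, 5/10, has an exact 95% CI of 18.7% to 81.3%.

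**The case against.** The strongest reply is that a partly coherent reading exists. The listed items are the domains, the three categories grade the overall result, 3.4 has the physician assign the grade at month 1, and 8.4.1 reports the top grade. If a 50% response is then taken to mean complete response, the rule can be applied to neurologic patients too. That reading is available, but the protocol does not state it. It also leaves the endpoint labelled primary in two sections without an analysis.

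Some stronger conclusions that a reader might infer do not follow:
- *That 8.4.1 makes complete response the sole primary variable.* It is the first of four, unranked.
- *That a 50% response is meaningless for neurologic patients.* A 50% change could be computed on CRP or on the 10-cm global VAS, both among the neurologic items in 2.1. What is missing is a statement of which measure counts.
- *That the ITT result could be hidden.* Section 8.1 presents both sets, so it will be shown. Redacted text stands just before that sentence, so 8.1 may once have said more about the main set. Section 8.4.2, which shows no redaction, names none.
- *That the absence of a null hypothesis, error rate or power calculation is an error.* Section 8.1 says that the trial is exploratory and not powered, which is acceptable for a pilot.
- *That a definition was or will be picked after the fact.* The documents leave room for it and show nothing more.

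The exploratory label and the soft verb in 8.4.2 lessen the weight of the rule. They do not supply the missing definition behind a sentence that sets a condition for claiming efficacy.

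**Conclusion.** The point holds. The any-item endpoint labelled primary in 2.1 and 5.9.1 is absent from the primary variables in 8.4.1, no section names a success category, and the 8.4.2 rule has no defined value for neurologic patients and no stated denominator. The possible effect spans the whole scale: 10/10 against 0/10 when every patient improves only partially. Those are two scorings of the same assumed patients, not independent samples, so the separation of their intervals is not evidence of anything further. The probabilities of 0.63 to 0.96 rest on assumed response rates and on complete-or-partial response standing in for any-item. The shift from 40% to 67% rests on assumed counts and on all six continuing patients completing without major deviations. The contradiction in the text rests on none of these assumptions. It should be resolved before Day 30 data are summarised.

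**What to change.** **Primary variable.** In 2.1, 5.9.1, 8.4.1 and 8.4.2, use one variable: the proportion of ITT patients who meet one named success definition at Day 30, set out for each type of involvement. Report it overall and by involvement with exact 95% confidence intervals. Complete response, listed first in 8.4.1, is workable. Any-item improvement, already labelled primary, is also acceptable, although a fall in inflammatory markers alone can satisfy it. Report the definition not chosen, and complete-or-partial response, beside it on the same ITT denominator. Move VAS, BDCAF and steroid tapering to secondary.

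**Rule.** In 8.4.2, replace the 50% response with the named definition, state that the ITT set decides, and describe a positive result as a signal for further study.

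**Counting rules, for analysis only.** State how to count patients with both involvements (Section 4.1 admits them), patients given rescue treatment before Day 30 (5.5.6), patients who fit no response category, and neurologic patients without Day 30 CSF, since the assessment schedule marks the puncture optional. Keep this last group in the denominator and add a sensitivity analysis. Give the analysis classification its own label, because it may differ from the physician's month-1 category.

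**Left to the sponsor.** The vascular cut-offs in 2.1 and 5.9.1 conflict at exactly 50% and must be reconciled. They decide month-1 treatment under 3.1 and 5.5.5, so no cut-off is proposed here.

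**Cost.** Apart from the cut-offs, this is a wording amendment with no new visits or data. If complete response is chosen, the endpoint now labelled primary is demoted and the bar is stricter, especially for neurologic patients, who would need full recovery, lesion disappearance and normal CSF by Day 30. If missing CSF is then counted as not complete, each patient who would otherwise be a complete responder lowers the result by 1/10 = 10 percentage points, which the sensitivity analysis would show. The conclusion becomes a signal rather than a claim.

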## 1 Introduction

### 1.1 Background

BD is a multisystem inflammatory disorder characterised by relapsing/remitting manifestations with variable vessel vasculitis as the underlying pathology. Prevalence of BD is in a wide range between 1-420 / 100,000 depending on geographic region in the world.

Some courses of the disease carry a higher unmet need:

a. Neurologic involvement: The patients experiencing parenchymal neurologic inflammatory attacks mainly affecting the brainstem have serious morbidity and increased mortality. There is no established treatment or a clinical trial conducted to evaluate the efficacy of any drug in Neuro-Behçet disease (NBD).

b. Vascular disease: Depending on the involved large vessels (arteries and/or veins), vascular involvement has also been associated with increased morbidity and mortality. Similar to NBD there is no established treatment or a clinical trial conducted to evaluate the efficacy of any drug in large vessel vasculitis.

In recent years, some case reports showed the efficacy of canakinumab in different BD manifestations. (1,2,3,4)

Vitale et al. reported that the prompt and sustained clinical efficacy of canakinumab as a monotherapy in patients with BD supports the opportunity of using this specific anti-IL-1 $\beta$  agent as a valid therapeutic option for those cases showing a disease course resistant or refractory to multiple treatments. (1)

Cantarini et al. reported the results of canakinumab treatment in a refractory patient with BD, which was well-tolerated, and at the 6-month follow-up, no adverse events were noted. (2)

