### 3 Investigational plan

#### 3.1 Study design

The study will be conducted as an exploratory open-label pilot trial. There will be only one treatment arm. The improvement will be evaluated in comparison to the findings recorded at the baseline.

Figure 3-1 Study design

Approximately 10 subjects aged 18 to 60 years, who sign an informed consent and meet all inclusion and exclusion criteria in the screening period will enter into the study. The first dose of canakinumab will be administered as 300 mg IV.

At the end of the first month, an analysis will be conducted to assess the complete, partial, and non-responders to canakinumab treatment by physician.

Partial responders will be able to take the 2nd canakinumab dose as 300 mg IV infusion at the first month then will continue the canakinumab treatment with 150 mg IV infusions at monthly intervals for 4 times. The complete responders will continue the canakinumab treatment with 150 mg IV infusions at monthly intervals for 5 times. Non-responder or deteriorating patients will be dropped from the study at the first month evaluations.

At month 6, the patients will be able to switch to SC injections or continue as IV infusions of 150 mg canakinumab for additional 6 monthly administrations. Non-responder or deteriorating patients will be dropped from the study at the first month evaluations.

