### 4.1 Inclusion criteria

**Key inclusion criteria :** Biologic-naïve patients with BD fulfilling the ISG criteria, who have a recent exacerbation of large-vessel vascular disease and/or parenchymal neurologic disease within the last month.

**For NBS :1)** Patients experiencing an acute exacerbation of parenchymal neurologic disease involving brainstem and/or diencephalic region with in last month.

Exacerbation is defined based on the presence of both of the following:

- a. An acute/subacute neurological syndrome including any of hemiparesis, ataxia, dysarthria within the first month of onset of neurologic manifestations (without any prior high dose steroid treatment)
- b. Compatible cranial MRI lesion involving brainstem and/or diencephalic region

**2)** Patients aged over 18-60 BD fulfilling the International Study Group (ISG) criteria, who have exacerbation of large-vessel vascular disease and/or parenchymal neurologic disease *with in last month*.

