#### **For Vascular Disease :**

1)Patients experiencing an acute exacerbation of vascular disease within the last month, involving

- d. Large arteries (abdominal aorta, pulmonary arteries, extremity arteries)
- e. Large veins (deep vein thrombosis of extremities, caval vein thrombosis, dural sinus thrombosis)
- f. Compatible radiological findings (spiral CT, MR, or Doppler ultrasonography)

**2)** Patients aged over 18-60 BD fulfilling the International Study Group (ISG) criteria, who have exacerbation of large-vessel vascular disease and/or parenchymal neurologic disease *with in last month*.

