### 5.10.6 CSF Collection

CSF analyses that were performed within 3 weeks before the study entry could also be used. CSF cell count analysis will be performed in the local laboratory [REDACTED]

Each CSF sample will consist of 1 mL to be collected in a sterile polypropylene tube that contain no preservatives. After collection, the sample may be stored at 4°C. However, it must be processed to centrifugation within 1 hour of the lumbar puncture. Longer storage times at 4°C must be documented accordingly in the source documents and CRF. [REDACTED]

Sample tubes are centrifuged at 4000 x g for 10 minutes at 4°C to pellet cells and other insoluble material. The supernatant is then transferred to a new sterile polypropylene tube and gently mixed by inversion. Two (2) aliquots (0.5 mL) of the supernatant are dispensed to 0.5 mL polypropylene cryovials. This procedure limits oxidation effects by minimizing empty space in the cryovials. The 0.5 mL cryovials containing the CSF aliquots as well as the polypropylene tubes containing the cell pellets are immediately placed on dry ice.

Once completely frozen, the tubes are transferred to a freezer for storage below -70°C until shipment to the central lab. The samples must be packed on sufficient dry ice for shipment to the central lab without thawing. Upon arrival at the central lab, CSF samples must be stored below -70°C. Any thawing of frozen samples must be avoided.

Sampling problems will be noted in the CRF as an attached note.

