### **8 Data analysis**

#### **8.1 Analysis sets**

Investigators will enter the information required by the protocol into the Novartis Case Report Forms (CRFs). Non-obvious errors or omissions will be entered on Data Query Forms, which will be returned to the investigational site for resolution.

The data from all centers will be pooled and summarized with respect to demographic and baseline characteristics and efficacy and safety observations. [REDACTED]

[REDACTED] Data will be presented for the complete intent-to-treat population (all subjects having taken at least one dose of study medication) as well as the per-protocol population (all subjects who completed the study without major protocol deviations). Safety data will be evaluated for the safety population (all subjects having taken at least one dose and who have at least one post-baseline assessment).

Data summaries will be presented.

This trial is an exploratory study, and it is not powered for a statistical analysis. The statistical analyses of the measurements will be performed when possible, and these analysis will be done by the investigators and an independent Contract Research Organization.

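### Section 8.4.2 lets an uncontrolled change from baseline support an efficacy claim, a condition that continuing natural recovery can also meet

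*Combined protocol and SAP*

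**What the plan says.** Section 8.4.2 gives the decision rule. It opens with the words "To claim the efficacy of canakinumab on the resolution of attacks" and then sets the aim: a response of 50% or more in half or more of the patients. The same section makes baseline the reference for every parameter. Section 3.1 agrees: "The improvement will be evaluated in comparison to the findings recorded at the baseline". Section 3.3 rules out an active comparator, and no section gives a historical or natural-history response rate.

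On the disease and the timing of entry, Section 1.1 states: "BD is a multisystem inflammatory disorder characterised by relapsing/remitting manifestations". The vascular entry criterion in Section 4.1 reads "Patients experiencing an acute exacerbation of vascular disease within the last month, involving". The neurologic criterion sets a similar one-month limit and adds the condition "without any prior high dose steroid treatment". Response is read at Day 30 (Sections 2.1 and 5.9.1).

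On the standing of the trial, Section 8.1 says: "This trial is an exploratory study, and it is not powered for a statistical analysis". Section 8.7 gives a sample size of 10 and rests it on the exploratory purpose alone.

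**The concern.** Patients enter because they have recently flared, and they are assessed a month later. In a disease that relapses and remits, some will improve over that month whatever they are given. No entry criterion requires the flare to be stable or worsening at Day 0, and Section 4.2 forbids the investigator to add exclusions. A patient who is already improving can therefore enter, and the improvement that continues after Day 0 counts as response.

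A single-arm pilot may accept this, provided that it reports what it saw and claims no more. Section 8.4.2 goes further and says when efficacy may be claimed. Nothing in the plan states how many responders would be expected without the drug, so a result that meets the rule cannot be attributed to canakinumab. At stake is an efficacy statement in the study report that the design cannot support.

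**Working it through.** **Inputs from the documents.** Sample size 10 (Sections 3.1, 5 and 8.7). Success mark: half or more of the patients, so 5 of 10 (Section 8.4.2). Reference: own baseline (Sections 3.1 and 8.4.2). Assessment at Day 30 (Section 2.1).

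**The plan's own figure.** The sample size of 10 cannot be reproduced: no null rate, target rate, error level or power is given for it.

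**Assumption.** Let p be the probability that a patient reaches the required response by Day 30 with no drug effect. The documents do not give p, so a range is shown. Patients are treated as independent with a common p.

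**Formula.** P(claim) = P(X ≥ 5) = Σ over k = 5 to 10 of C(10,k) · p^k · (1−p)^(10−k).

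Two cases written out:
- p = 0.5: (252 + 210 + 120 + 45 + 10 + 1)/1024 = 638/1024 = 0.623.
- p = 0.2: 0.02642 + 0.00551 + 0.00079 + 0.00007 + 0.000004 + 0.0000001 = 0.0328.

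| Assumed p | P(5 or more of 10) |
|---|---|
| 0.1 | 0.2% |
| 0.2 | 3.3% |
| 0.3 | 15.0% |
| 0.4 | 36.7% |
| 0.5 | 62.3% |
| 0.6 | 83.4% |

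**Break-even.** Solving P(X ≥ 5) = 0.05 gives p = 0.222. Above a background rate of about 22%, the chance of a false claim exceeds 5%.

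**Precision.** For exactly 5 of 10, the Clopper-Pearson 95% interval runs from the 0.025 quantile of Beta(5, 6) to the 0.975 quantile of Beta(6, 5): 18.7% to 81.3%.

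**Sensitivity to the number enrolled.** Section 3.1 says the number is approximate. With the mark at half the patients, rounded up:

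| Patients (mark) | p = 0.2 | p = 0.3 | p = 0.4 | p = 0.5 |
|---|---|---|---|---|
| 8 (4) | 5.6% | 19.4% | 40.6% | 63.7% |
| 9 (5) | 2.0% | 9.9% | 26.7% | 50.0% |
| 10 (5) | 3.3% | 15.0% | 36.7% | 62.3% |
| 11 (6) | 1.2% | 7.8% | 24.7% | 50.0% |
| 12 (6) | 1.9% | 11.8% | 33.5% | 61.3% |

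The conclusion does not depend on the exact number.

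**What a justified mark would need.** With 10 patients and one-sided error at or below 5%, the smallest number of responders is 5 if p = 0.2, 6 if p = 0.3, 8 if p = 0.4 and 9 if p = 0.5. The mark of 5 is adequate only at the low end of the range.

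**The case against.** The strongest reply is that this is a declared exploratory pilot. Section 8.1 says that it is not powered, Section 8.4.2 words the 50% level as an aim, and no hypothesis or error rate is stated. That no uncontrolled pilot can separate drug effect from natural course is a general remark and no defect of this plan. This stands as a defence of the design, and no control arm is asked for. It does not defend the sentence in Section 8.4.2, which no other section withdraws or qualifies.

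The reply is also right that p may be low. Section 1.1 speaks of serious morbidity, and Section 5.7.4 of a life-threatening course. Neurologic complete response needs full recovery, disappearance of MRI lesions and normal CSF, which is hard to reach unaided. Section 8.4.1 lists the percentage of complete responders, but Section 8.4.2 does not tie its 50% response to that category.

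A reader might infer more than the documents support:
- **That natural recovery will meet the rule.** It can; how often depends on a rate that the documents do not give.
- **That no external recovery rate exists.** Section 1.1 says that no drug trial has been done. That does not show that natural-history data are lacking, only that the plan cites none.
- **That improvement before the drug is counted.** A Day 0 reference removes it. Only recovery that continues after Day 0 counts.
- **That an old CSF sample can create a responder.** Section 5.10.6 says "CSF analyses that were performed within 3 weeks before the study entry could also be used", so a fall in cell count may predate the drug. But neurologic partial response also needs clinical improvement and smaller MRI lesions, and vascular response does not use CSF.
- **That earlier oral steroid inflates vascular response.** The vascular criteria lack the neurologic bar on high-dose steroid, and Section 5.5.8 limits higher doses only from one week before Day 0. Carry-over could help the Day 30 result, but it could also lower Day 0 CRP and VAS and make a 50% fall harder. The direction is unknown, and different entry conditions for two subtypes are not in themselves a contradiction.

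**Conclusion.** The point holds for the claim, not for the design. Section 8.4.2 permits an efficacy claim on a result that continuing natural recovery can produce. With 10 patients the probability of that is 3% if the background rate is 0.2, and it rises to 83% at 0.6. It is at or below 5% only if the rate is about 22% or lower, which the plan does not argue. The figures rest on a mark of 5 of 10, independent patients with a common rate, and a range of rates that is assumed throughout. The documents do not support saying that the rule would be met by recovery alone, or that prior steroid or an old CSF sample biases the result in a known direction. The change should be made because, as written, the rule permits a conclusion that the data cannot carry.

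**What to change.** **In Section 8.4.2**, replace the efficacy claim with a descriptive statement: the Day 30 responder proportion is reported as an uncontrolled estimate with an exact 95% confidence interval, and the 50% mark serves only to inform whether a controlled study is worthwhile.

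**Beside it, for reporting only**, list each Day 30 response with:
- time from attack onset to first dose;
- systemic steroid use before Day 0;
- a flag where the reference CSF predates the screening window (Day -7 to 0).

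Also show the Screening-to-Visit 1 change in symptom VAS, CRP, ESR, SAA and BDCAF where the two visits were separate. The assessment schedule has these at both visits. The physician and patient global assessments start at Visit 1 and cannot be used this way.

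The response categories themselves stay as they are. Under Sections 3.1 and 5.5.5 they guide treatment after Day 30, so the listing must not alter them.

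**Cost.** A change of wording, one listing and a short summary; no new arm or visit. Section 5.8 specifies medication name and reason, and no section names onset date as a CRF item, so onset date and the dose and dates of earlier steroid may need a CRF field. The downsides are a weaker claim and a pre-dose trend that covers at most 7 days and is missing where Screening and Visit 1 are combined.

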## **8.7 Sample size calculation**

Because of exploratory nature of the study, 10 patients will provide information.

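### Section 8.4.2 ties an efficacy claim to an observed responder share of at least 50% in about 10 patients, with no planned interval, in a study the plan calls exploratory and unpowered

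*Combined protocol and SAP*

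**What the plan says.** Section 8.4.2, which carries the statistical model and hypothesis, begins "To claim the efficacy of canakinumab on the resolution of attacks" and then sets the condition: "at least 50% response will be aimed in at least 50% of the patients". It names no reference rate, test, interval or significance level. The first variable listed in 8.4.1 is "Percentage of complete responders".

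For categorical variables, section 8.5.1 says only: "Categorical variables will be summarized by absolute frequencies and percentages". The 0.05 level in that section belongs to the Wilcoxon signed rank test of pre-treatment against post-treatment values, not to a proportion.

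On size, section 3.1 gives "Approximately 10 subjects aged 18 to 60 years" and adds "There will be only one treatment arm". Section 8.7 reads: "Because of exploratory nature of the study, 10 patients will provide information". Section 8.1 states: "This trial is an exploratory study, and it is not powered for a statistical analysis".

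**The concern.** Read as a condition for a claim, 8.4.2 takes one input, the observed share of responders, and makes no allowance for sampling error. With about 10 patients that error is large. It would remain even if every response were measured correctly and caused by the drug.

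The sections also pull apart. Section 8.1 disclaims statistical power, while 8.4.2 reserves the right to claim efficacy from a point estimate. Followed as written, the plan lets 5 responders out of 10 be reported as efficacy without any planned statement of precision next to the percentage.

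**Working it through.** **Inputs**
- N = 10 (sections 3.1 and 8.7; 3.1 says approximately, so 8 to 12 is also shown).
- Threshold: observed share of at least 50% (8.4.2), which is 5 of 10.
- Confidence level: none is given for a proportion. I assume two-sided 95%.
- Responder rate without a drug effect: none is given. A range of true rates is shown.
- Each patient is treated as a responder or not. The plan does not map its 50% response onto the complete and partial categories, so this too is an assumption.

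The plan has no derivation to reproduce, because the sample size is stated without inputs.

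**Step 1. What 5 of 10 tells us.** The exact (Clopper-Pearson) lower limit is the rate p at which P(X ≥ 5 | 10, p) = 0.025. At p = 0.187 this probability is 0.02495, so the lower limit is 18.7%. By symmetry at 5 of 10 the upper limit is 100% − 18.7% = 81.3%. Other methods give lower limits of 19.0% (Wald), 22.4% (Jeffreys) and 23.7% (Wilson), so the choice of method changes little.

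**Step 2. How often the condition is met.** P(X ≥ 5) = Σ C(10,k) p^k (1−p)^(10−k) for k = 5 to 10. At p = 0.5 this is (252 + 210 + 120 + 45 + 10 + 1)/1024 = 638/1024 = 0.623. Across true rates:

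| True rate | P(5 or more of 10) |
|---|---|
| 19% | 2.7% |
| 20% | 3.3% |
| 30% | 15.0% |
| 40% | 36.7% |
| 45% | 49.6% |
| 50% | 62.3% |
| 70% | 95.3% |

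**Step 3. Sensitivity to N.** For each N the threshold is the smallest count that reaches half.

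| N | Threshold | Exact 95% CI at threshold | P(met) at a true rate of 40% |
|---|---|---|---|
| 8 | 4 | 15.7% to 84.3% | 40.6% |
| 9 | 5 | 21.2% to 86.3% | 26.7% |
| 10 | 5 | 18.7% to 81.3% | 36.7% |
| 11 | 6 | 23.4% to 83.3% | 24.7% |
| 12 | 6 | 21.1% to 78.9% | 33.5% |

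The picture is the same throughout: a wide interval at the threshold, and a 25% to 41% chance of meeting it when the true rate is 40%.

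**The case against.** The strongest reply is that the plan already discloses the limitation. It calls the trial an exploratory pilot and says it is not powered, and everyone knows that 10 patients give a wide interval. The verb in 8.4.2 expresses an aim, so the sentence may be a target rather than a sufficient decision rule. Counts will be reported, so a reader can compute an interval, and 8.1 leaves room for statistical analysis where possible.

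Much of this stands, and it lowers the weight of the point. It does not remove it. The sentence still opens by naming what is needed to claim efficacy, and that does not fit the disclaimer in 8.1. If a target was meant, saying so costs nothing. An interval that a reader could work out is not the same as one that the plan commits to report.

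Three stronger readings are tempting, and the documents do not support them:
- A reader might infer from the 19% lower limit that the condition would readily pass a drug with a true rate near 19%. It would not: it is met in 2.7% of trials at that rate. The limit is the edge of what 5 of 10 allows, not a likely value.
- A reader might call the 37% at a true rate of 40%, or the 62% at 50%, a false-positive rate. That makes 50% a null hypothesis. The plan gives 50% as an aim and states no rate that counts as no effect.
- A reader might conclude that the claim should require a lower bound above 50%. At N = 10 that means 9 responders: the one-sided 95% lower bound is 49.3% at 8 of 10 and 60.6% at 9 of 10. Such a rule would be met in only 15% of trials at a true rate of 70%, 38% at 80% and 74% at 90%. That would place a confirmatory test on a pilot that disclaims power.

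**Conclusion.** The point holds as one of wording and reporting. Section 8.4.2 permits an efficacy claim from 5 responders in 10, a result compatible with true rates from 19% to 81%, and no interval is planned to accompany it. The practical weakness lies in the range moderately below the target: the condition is met in 37% of trials at a true rate of 40% and in 50% at 45%, against 62% at 50%. It does screen out very low rates, with about 3% at 19% to 20%.

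This rests on three assumptions: a two-sided 95% level, a clear responder or non-responder status for each patient, and 8.4.2 being used as the condition for a claim. Changing the interval method moves the lower limit only between 19% and 24%. The exploratory status does not excuse the claim wording; it is the reason that wording does not fit.

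**What to change.** In 8.4.2, replace the efficacy-claim wording with a descriptive target of 50%, to be reported as met or not met. Report responders as x/N of all dosed patients, with the exact (Clopper-Pearson) 95% confidence interval. Naming that denominator also matters because 8.1 presents both an intent-to-treat and a per-protocol population and does not say which one governs the target. In 8.5.1, add the same interval to the summaries of categorical variables. Do not add a 9-of-10 success rule.

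The cost is a change of wording and one extra table column, with no additional patients or procedures. The real downside is that a result at or just above 50% could no longer be reported as an efficacy claim; it would read as target met, with an estimate and its interval.
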